## 4. SAFETY

Continuous variables will be summarized using the following statistics, as appropriate: number of observations, arithmetic mean (mean), 95% CI for the mean, standard deviation (SD), standard error (SE), median, quartiles (Q1 and Q3), minimum and maximum. Frequencies and percentages (to one decimal place) will be generated for categorical variables.

Safety data will be summarized in each period of the active phase. Only SAEs will be tabulated for all phases, including the non-active phases. The analysis phases are defined in section 2.1. Denominator for the percentages is the number of subjects in the considered population and period for a certain regimen (incidence per 100 subjects/period).

*Note:* Safety data post-dose 3 in the control group will be presented separately for Nimenrix and placebo, unless otherwise specified (section 5.2).

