9.1.3.2.2. Post-vaccination Follow-Up

9.1.3.2.2.1. Post-first, Post-second and Post-third Vaccination Follow-Up

Visits 3 and 4 (3 and 7 Days Post-first Vaccination), Visits 6 and 7 (3 and 7 Days Post-second Vaccination) and Visits 9 and 10 (3 and 7 Days Post-third Vaccination)

Visits 3, 6 and 9 at 3 days post-vaccination will be a telephone call to check subject diaries and to collect safety information (solicited and unsolicited AEs, SAEs, concomitant medications, and RTIs).

Visits 4, 7 and 10 at 7 days post-vaccination will include an abbreviated physical examination (at the discretion of the investigator), vital signs measurement, and recording of any (serious) AEs, concomitant medications and RTIs. The subject diary will be reviewed and collected. If Visit 4 occurs before the end of Day 8, Visit 7 occurs before the end of Day 36 or Visit 10 occurs before the end of Day 64 (ie, before the end of the post-vaccination diary period), review of the diary will still take place, but the diary will be returned by the subject's parent/guardian or caregiver at the next visit (ie, Visit 5, Visit 8 or Visit 11, respectively).

A blood sample for immunogenicity assessments will be collected from all subjects 7 days post-first vaccination.

Note: If any subject comes in earlier than Day 8 for Visit 4, Day 36 for Visit 7 or Day 64 for Visit 10 (allowed windows are -1/+3, ± 2 days, and ± 2 days, respectively), a subsequent phone call will be made at the end of the diary period to collect diary card information recorded between the actual visit and the end of the diary period (ie, Day 8, Day 36 or Day 64, respectively).

9.1.3.2.2.2. Post-last Vaccination Follow-Up

Visits 11 and 12 (28 Days and 6 Months Post-third Vaccination)

Visits 11 and 12 will include an abbreviated physical examination including vital signs measurement (at the discretion of the investigator), measurement of length and weight, recording of unsolicited AEs (Visit 11 only), any RTIs, any SAEs, concomitant medications, and any MA-RTIs.

Samples for immunogenicity assessments will be collected at Visit 11.

A nasal sample will be collected 28 days post-final vaccination from all subjects at Visit 11.

Parents/legal guardians or caregivers (where allowed by local regulations) will be invited to complete an Institutional Review Board/Independent Ethics Committee (IRB/IEC) approved Participant Experience Survey at Visit 12 (See Section 9.2.4).

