## 1. INTRODUCTION

An independent data monitoring committee (IDMC) will be established in the study VAC18194RSV2002 to review safety data and to ensure the continuing safety of the subjects enrolled in this study.

This statistical analysis plan (SAP) contains the derivations and statistical methods for the analysis to be conducted for the IDMC. There is one planned IDMC analysis in the current study, to be performed on Day 8, after the first dose in the first 12 toddlers (6 receiving the active vaccine and 6 receiving placebo). Snapshot data will be used—The database will be cleaned on an ongoing basis, there will be no formal data cleaning for the IDMC analyses.

The IDMC will review unblinded data. An external statistician (the statistical support group (SSG) statistician) independent of the sponsor and not involved in the interim, primary, and final analyses of the study will prepare the data and perform all analyses for review by the IDMC .

Details on each table, graph and listing to be generated for the IDMC is described in a separate data presentation specifications (DPS) document. However, the study team or IDMC may request additional deliverables, with this SAP serving as a guidance. Safety data from the interim (if applicable), primary and final analyses will also be shared with the IDMC.

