**Table 2: Analysis Phases and Periods**

Phase	Phase #	Period	Period #	Interval	
				From	To
Screening	1			Date and time of signing the informed consent form a	One minute prior to first vaccination
Regimen	2	Post-dose 1	1	Date and time of first vaccination	Minimum of: a) 23:59 at the date of last contact (for early discontinuation) b) 23:59 at the date of database cut-off date in case of interim analysis c) One minute prior to second vaccination. If second vaccination was not administered, then use maximum of (Day 28 after the first vaccination at 23:59, scheduled visit 28 days after first vaccination at 23:59)
Regimen	2	Post-dose 2	2	Date and time of second vaccination	Minimum of: a) 23:59 at the date of last contact (for early discontinuation) b) 23:59 at the date of database cut-off date in case of interim analysis c) One minute prior to third vaccination. If third vaccination was not administered, then use maximum of (Day 28 after the second vaccination at 23:59, scheduled visit 28 days after second vaccination at 23:59)
Regimen	2	Post-dose 3	3	Date and time of third vaccination	Minimum of: a) 23:59 at the date of last contact (for early discontinuation) b) 23:59 at the date of database cut-off date in case of interim analysis c) Maximum (Day 28 after the third vaccination at 23:59, scheduled visit 28 days after third vaccination at 23:59)
Follow-up	3			One minute after the end of the last post-dose period	Minimum of: a) 23:59 at the Date of last contact b) 23:59 at the date of database cut-off date in case of interim

a In case an earlier date is available (e.g. for vital signs), then use the very first date to include all data in the screening phase.

Adverse events will be allocated to the above phases and periods, see details in section 4.1. The regimen phase (post-dose 1, post-dose 2 and post-dose 3 periods) is considered the active phase, the screening and follow-up phase are considered non-active phases.

For descriptive statistics over time, assessments (regardless of the investigated parameter) will be allocated to an analysis visit based on the planned visit as captured in the database.

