## **2.3. Analysis Sets**

### **2.3.1. Full Analysis (FA) Set**

The FA set includes all subjects who were randomized and received at least one dose of study vaccine, regardless of the occurrence of protocol deviations. All safety analyses will be based on the FA set.

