#### **4.1.3. Handling of Missing Data for Adverse Events**

Missing data will not be imputed.

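### SAP Section 4 divides every safety percentage in the IDMC outputs by all vaccinated children in the period, so a child with no solicited-AE assessment or vital-sign reading counts as unaffected

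*SAP*

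**What the plan says.** SAP Section 4 gives a single rule for safety percentages: "Denominator for the percentages is the number of subjects in the considered population and period for a certain regimen". Section 2.3.1 defines the population: "The FA set includes all subjects who were randomized and received at least one dose of study vaccine, regardless of the occurrence of protocol deviations". It adds: "All safety analyses will be based on the FA set". In SAP Table 2 the post-dose 1 period starts at "Date and time of first vaccination", and the later periods start at the second and third vaccinations. Receiving the dose is therefore enough to enter the divisor.

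The numerator, in SAP 4.1.2, is the number of subjects with at least one event of the given kind, for solicited and unsolicited events alike. Under SAP 4.1.1, solicited events are analysed from the investigator's overall assessment of each child in each reporting period, which includes whether the event occurred at all. SAP 4.2 tabulates temperature in half-degree steps, and the number and percentage outside limits for respiratory rate, pulse and SpO2.

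None of these sections gives its own divisor. The number of observations is listed only for continuous variables. On missing adverse event data, SAP 4.1.3 says: "Missing data will not be imputed".

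SAP Section 1 confines the document to analyses for the IDMC. One is planned, after the first dose in the first 12 children (6 per arm), on a data snapshot for which "there will be no formal data cleaning for the IDMC analyses".

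**The concern.** A solicited event has three possible states: observed, not observed, and not assessed. A divisor of all subjects in the period merges the last two. The SAP says that nothing is imputed, but a child without an assessment is handled as if the answer were no. The same happens to a child without an SpO2, pulse or respiratory rate reading, who is counted as within limits. In the temperature table a child without a reading falls into no interval but still enlarges the divisor, so the fever intervals read low.

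For unsolicited events and SAEs, which are collected by report, an all-vaccinated divisor is conventional and is not in question.

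For solicited data the shift can only be downward, which is the unfavourable direction for a safety review. Solicited events are the first-listed primary endpoint, and fevers in a related study led to the dose reduction in Amendment 2. In a review of 6 against 6, one unassessed child is a sixth of an arm, and chance imbalance in missing data would also distort the comparison between arms.

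**Working it through.** The plan states no figure on this point, so there is none to reproduce.

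**Inputs**
- Divisor N: all Full Analysis subjects in the period (SAP 4, 2.3.1, Table 2).
- N = 6 per arm at the planned IDMC analysis (SAP 1). N = 18 per arm in the current design (Protocol 3.1, Table 4), used here for scale only.
- m, the number of unassessed children: not given in the documents. Assumed 0 to 2 for N = 6 and 0 to 3 for N = 18.
- True reaction rate r: not given. Assumed 20%, 50% and 60%.

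**Step 1: an observed count.** With x reactors among the N − m assessed children, the SAP reports x/N, and the rate among assessed children is x/(N − m). Since N ≥ N − m, the SAP figure is never the larger.
- N = 6, m = 1, x = 3: 3/6 = 50.0% against 3/5 = 60.0%.
- N = 6, m = 1, x = 2: 2/6 = 33.3% against 2/5 = 40.0%.

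**Step 2: what the missing child could be.** With x = 3, N = 6, m = 1, the true proportion in all six is 3/6 = 50.0% if the unassessed child had no reaction and 4/6 = 66.7% if there was one. The SAP figure is the lowest value that the data allow.

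**Step 3: expected size.** If missingness is unrelated to reactions, the expected reported percentage is r × (N − m)/N.

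| N | m | r = 20% | r = 50% | r = 60% |
|---|---|---|---|---|
| 6 | 0 | 20.0% | 50.0% | 60.0% |
| 6 | 1 | 16.7% | 41.7% | 50.0% |
| 6 | 2 | 13.3% | 33.3% | 40.0% |
| 18 | 1 | 18.9% | 47.2% | 56.7% |
| 18 | 2 | 17.8% | 44.4% | 53.3% |
| 18 | 3 | 16.7% | 41.7% | 50.0% |

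For example, 0.60 × 5/6 = 0.50. The relative shortfall is m/N, or 1/6 = 16.7% for one child in six. At m = 0 the two divisors give the same answer.

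**The case against.** The strongest reply is that few assessments should be missing. Under Protocol 9.1.3.2.1 and 9.1.3.2.2, site staff document solicited events after the post-dose observation, a day-3 call checks the diary, and a day-7 visit reviews it. The analysis rests on the investigator's assessment, not on receipt of the paper diary. This stands: it limits the likely size, though it does not change how the rule treats a child who is not assessed.

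Several stronger readings are tempting, but the documents do not support them.

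- A reader might infer that an early day-7 visit leaves a child unassessed, because the diary comes back only at the next visit. The protocol says that "review of the diary will still take place, but the diary will be returned" later, and requires a telephone call at the end of the diary period to collect the remaining entries. That child is assessed.
- A reader might infer that a Day 8 snapshot cuts off children seen late in the visit window (up to Day 11). Protocol 3.1 describes a review of 7-day data in the first 12 subjects. Nothing places the snapshot before the last of those visits, and uncleaned data are not the same as absent data.
- A reader might point to remote visits under Protocol Attachment 3. It came with Amendment 6, when 37 children were already enrolled, so it is hard to tie to the first 12. It also asks for safety data by interview at each contact.
- A reader might carry the point over to the primary and final analyses. This SAP covers IDMC outputs only. Protocol 11.7 does not restrict percentages to assessed children either, but that does not show which divisor those analyses will use.
- A reader might expect the pausing rules to be weakened. Those in Protocol 11.10 count subjects and use no percentages.

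Two further objections stand in part. If unassessed children truly had no reaction, the SAP figure is right and the assessed-only figure is too high; this is a reason to print both numbers. The separate data presentation specifications, which are not available here, may show the number assessed. If they set a different divisor, they would conflict with the SAP's general rule, which would still need correcting.

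**Conclusion.** The point holds as a conditional one. As written, SAP Section 4 treats a missing solicited-AE assessment or vital-sign reading in the IDMC outputs as a negative finding. Whenever such data are missing, the percentage is at or below the rate among assessed children. At 6 per arm, one unassessed child turns an assumed 60% into an expected 50%, and an assumed 20% into 16.7%. These sizes rest on an assumed count of missing children and on missingness unrelated to reactions. With complete data the bias is zero.

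The text does not support saying that reactogenicity in this trial will be understated. It supports saying that the rule would understate it if assessments are missing, and that the IDMC could not tell from the percentage alone whether a child had no reaction or no data. This is a modest defect that is cheap to remove.

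**What to change.** In SAP Section 4, keep all Full Analysis subjects in the period as the divisor for unsolicited AEs and SAEs. For solicited AEs, temperature and the vital-sign limits, use the subjects in the period with at least one recorded assessment of that item. For solicited AEs, tie this to the investigator's overall assessment described in SAP 4.1.1, so that it is clear which record counts. Print both the number assessed and the number in the period, by arm, in each of these tables, and align the data presentation specifications.

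The cost is one SAP sentence and a denominator flag in the programs. The downside is that denominators may differ between rows of a table, which the printed counts make visible.

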#### 4.1. Adverse Events

The analysis of AEs will be based on the medical dictionary for regulatory activities (MedDRA) coded terms as provided in the clinical database.

##### 4.1.1. Definitions

The following safety and reactogenicity endpoints are the primary endpoints:

- Solicited local and systemic AEs for 7 days after each vaccination.
- Unsolicited AEs for 28 days after each vaccination.
- SAEs from first dose administration to the end of the study.

Solicited AEs are precisely defined events (local and systemic) that subjects are specifically asked about and which are noted by subjects in the diary. In each reporting period, the investigator will evaluate the solicited AEs (from diary) per subjects and will record the overall assessment in the CRF. These data will include whether a solicited AE was observed, its start and end date, maximum severity grade over the reporting period, causality and seriousness (Yes/No). The analysis of solicited AEs will be based on the overall assessment by the investigator, per subject per reporting period. By definition, all solicited AEs at the injection site (local) will be considered related to the study vaccine administration.

Unsolicited AEs are all AEs that a subject experienced but were not specifically asked about. For unsolicited AEs, only the AEs starting within the 28-day period following each vaccination will be presented in the safety tables, except for SAE, which will be captured and presented throughout the study.

The severity of the AEs (solicited and unsolicited) will be classified as Mild (Grade 1), Moderate (Grade 2), Severe (grade 3) or Potentially Life Threatening (Grade 4). See CTP 12.1.3 for details on the criteria for the AE severity classification.

#### Phase Allocation of Adverse Events

Solicited AEs will always be allocated to their respective post-dose period, they will not be attributed to the Screening Phase..

The analysis of unsolicited AEs includes the following two steps:

1. AEs are allocated to phases;
2. Overlapping /consecutive AEs within a phase are combined.

**STEP 1: Allocation of AEs to the phases (and respective periods)**

Adverse events in the SDTM database will be allocated to periods based on their start date/time.

- If the start date/time of an event falls between (or on) the start and stop date/time of a period, the AE is attributed to that period (treatment-emergent principle).
- In case of partial start or stop dates (i.e. time and/or day and/or month and/or year missing), the events are allocated to the periods using the available partial information on start and/or end date; no imputation will be done. If, for instance, for the AE start date only month and year are available, these data are compared to the month and year information of the periods. In case of a completely missing start date, the event is allocated to the appropriate period (post-dose 1), except if the end date of the AE falls before the start of the post-dose 1 period. This rule may lead to multiplication of the event as a consequence of its assignment to multiple periods.
- In case of a completely missing end date (for the calculation of duration), the date is imputed by the cut-off date of the analysis for subjects still ongoing in the study, and by the end date of the last period for subjects who discontinued or completed the trial. The imputed end dates will not be shown in the data listings.

**STEP 2: Combining Overlapping/consecutive AEs**

Overlapping/consecutive events are defined as events of the same subject with the same preferred term that have at least 1 day in overlap or for which the start date of an event is 1 day after the end date of the preceding event. Overlapping/consecutive events may be combined into one AE or not, according to the following rules:

- 1) In case a non-active phase (e.g. Screening, Follow-up) is followed by an active phase, and the overlapping/consecutive events start in both phases, they are allocated to their respective phase and are considered as separate events.
- 2) In case overlapping/consecutive events start within a single phase, they are considered as one and the same AE. The individual events that contribute to this AE are retained as individual records in the ADAM database but are assigned the same onset, phase, and total duration.
- 3) In case an active phase is followed by a non-active phase (e.g. Follow-Up), and the overlapping/consecutive events start in both phases, they are allocated to the active phase and are considered as one and the same AE. The individual events that contribute to this AE are retained as individual records in the ADAM database but are assigned the same duration, onset and active phase.
- 4) In case an active phase is followed by an active phase, and the overlapping/consecutive events start in both phases, they are allocated to their respective phase and are considered as separate AEs. The same rule applies for 2 non-active phases.

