**Remarks:**

1. Events can only be combined into one and the same AE if their start and stop dates are complete.

2. In case the completely missing end date is imputed (for phase allocation), this date is also considered as a complete date.
3. Time during the day is not considered when determining overlap of events.

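### SAP Step 2 combines adverse events by phase, but all three post-dose periods form one phase, so an event starting after dose 2 or 3 can take an onset before that dose

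*SAP*

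**What the plan says.** The SAP handles unsolicited events in two steps (Section 4.1.1).

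- **Step 1** works by period: "Adverse events in the SDTM database will be allocated to periods based on their start date/time".
- **Step 2, rule 2** works by phase: "In case overlapping/consecutive events start within a single phase, they are considered as one and the same AE". The records combined in this way "are assigned the same onset, phase, and total duration". Records qualify if they belong to the same child, carry the same preferred term, and either share at least one day or meet the condition that "the start date of an event is 1 day after the end date of the preceding event".
- **Step 2, rule 4** keeps events apart across two active phases: "In case an active phase is followed by an active phase, and the overlapping/consecutive events start in both phases".
- **Remarks** require complete dates for combining, with one extension: "In case the completely missing end date is imputed (for phase allocation), this date is also considered as a complete date".

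The text under Table 2 (Section 2.1) fixes what a phase is: "The regimen phase (post-dose 1, post-dose 2 and post-dose 3 periods) is considered the active phase". The periods abut. Post-dose 1 normally ends "One minute prior to second vaccination", and post-dose 2 ends in the same way before the third.

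Safety tables are produced per period of the active phase (SAP Section 4). For non-serious unsolicited events they show only those that start within 28 days of a vaccination (SAP Section 4.1.1).

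**The concern.** Allocation and reporting are by period, but combining is by phase. Rule 4 suggests that the authors wanted events after different doses to stay separate. With a single active phase, the situation that rule 4 describes cannot arise between doses. Rule 2 governs instead, and it carries the earliest onset forward to every record in the chain.

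In a three-dose safety study, the IDMC needs to know which dose an event followed. An event that began a day or two after dose 2 but carries an onset before dose 2 looks as if it could not have been triggered by that dose. Post-dose 3 control data are to be split into Nimenrix and placebo (SAP Section 4). A control event that started after Nimenrix could therefore be shown under an earlier placebo dose, if the period is taken from the combined onset.

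**Working it through.** The plan gives no figure to reproduce. The check applies Table 2 and Step 2 literally to hypothetical records, first combining by phase (as written) and then by period.

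**Inputs**
- Doses on Days 1, 29 and 57 (Protocol Section 3.1).
- Dose 2 may be given up to 10 days late for acute illness or fever (Protocol Section 10.3): 29 + 10 = Day 39.
- All records come from one child, have one preferred term and have complete dates.
- Duration = last day − first day + 1. Days after dose = onset day − dose day.

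| Case | Records (days) | Combined by phase, as written | Combined by period |
|---|---|---|---|
| A: dose 2 on Day 29 | 25–30, 31–34 | One event: onset Day 25, 25 − 1 = 24 days after dose 1; duration 34 − 25 + 1 = 10 | Two events: onset Day 25, duration 6; onset Day 31, 31 − 29 = 2 days after dose 2, duration 4 |
| B: doses on Days 29 and 57 | 25–30, 31–57, 58–60 | One event: onset Day 25; duration 60 − 25 + 1 = 36 | Three events, one per period: durations 6, 27 and 3 |
| C: dose 2 on Day 39 | 33–39, 40–43 | One event: onset Day 33, 33 − 1 = 32 days after dose 1; duration 43 − 33 + 1 = 11 | Two events: onset Day 33, duration 7; onset Day 40, 40 − 39 = 1 day after dose 2, duration 4 |

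**Reading the cases**
- In A and B, no onset remains after dose 2 or dose 3, although records started there.
- In C, the combined onset is 32 days after dose 1, beyond the 28-day window, so a non-serious event would drop out of the tables. Its second record began one day after dose 2. The first record would be in the database: Protocol Section 12.3.1 asks for late-onset events that are ongoing on the day of the next vaccination to be recorded.

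**What is explicit and what is inferred.** Rule 2 reassigns onset, phase and duration, so the onset shift is explicit. It does not mention period. A move from one per-dose table to another follows only if the period is re-derived from the combined onset, and the SAP does not say whether it is.

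**Size per child**
- Full enrolment, 18 per group (Protocol Table 4): 1/18 = 5.6 points. With the 24 per group still shown in SAP Table 1: 1/24 = 4.2 points.
- The 12-child review, 6 per group (SAP Section 1): 1/6 = 16.7 points, if all six have reached the period concerned.

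**The case against.** The strongest reply is about scope. This SAP covers the IDMC analyses only, and its one planned analysis is at Day 8 after dose 1, where there is no dose boundary to cross. The interim, primary and final analyses are not the IDMC statistician's work. The protocol leaves the anamnestic-response criteria to a SAP, and this one contains none, so the main analysis rules may well sit in a document not available here. A reader might infer that the primary endpoint results are distorted. The documents do not support that.

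Several further points also stand:
- Solicited events always stay in their own post-dose period.
- A reader might infer that recurrences on re-dosing are generally moved back. They are not. A recurrence after a full event-free day is not combined, unless the earlier record has no end date.
- A reader might estimate the frequency from the chance that one illness spans a dose. That measures the wrong thing. A single record that spans a dose is correctly allocated by its start. The problem needs a second same-term record that starts after the dose, and the documents give no rate for this.
- The pausing rules (Protocol Section 11.10) and the severe RSV-LRTI rule do not use combined records.
- Treating two back-to-back records as one illness is clinically defensible.
- A completely missing end date plausibly means that the event is ongoing, so Remark 2 is not wrong in itself.

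The scope argument does not dispose of the point. Protocol Section 3.1 foresees that slow recruitment may push the IDMC review past the first child's second or third dose, so the snapshot could hold later data. The SAP also defines post-dose 2 and 3 periods, and it is meant to guide further deliverables that the IDMC or study team may request.

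**Conclusion.** The rule is wrong as written, with limited practical weight. Under the SAP's own definitions, a same-term unsolicited record that starts after dose 2 or 3 can take an onset before that dose, and nothing in Step 2 prevents it. That the onset shifts is certain on a literal reading. That the event is counted under the earlier dose depends on how the period is derived, which the SAP leaves open.

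IDMC outputs that include data after dose 2 or 3 are affected, whether from a late first review or an ad hoc request. The planned Day 8 data after dose 1 are not. No effect on the primary analysis can be shown from these documents. The frequency is unknown, so the size can be stated only per child: 5.6 points at 18 per group, and 16.7 points at 6 per group.

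**What to change.** In Step 2, state that events in the Regimen phase are combined only when they start in the same post-dose period. Alternatively, define each post-dose period as its own active phase, so that rule 4 applies. Add that when records start in different periods, each keeps the period given by its own start date.

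Keep Remark 2 and apply it within a period. Once combining stops at the dose boundary, an imputed end date can no longer carry an onset across doses.

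The cost is a short wording change and a small programming change. The downside is that a continuous illness entered as two records across a dose will be counted once in each period. A footnote to the per-period tables can say so.
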